## 3. ABSTRACT

**Study Title:** Non-interventional post-authorization prospective cohort study evaluating the effectiveness of the additional risk minimization measures for filgotinib (Jyseleca®) use in patients with ulcerative colitis: a European multi registry-based study

Protocol version: v3.0 Date: 25-January-2024 Author, Affiliation: PPD

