## 8. **RESEARCH METHODS**

## 8.1. Study Design

This DUS is based on a non-interventional, post-authorization, prospective, multicountry, registry-based, longitudinal follow-up (cohort) design with secondary use of data collected from 3 European IBD registries. The registries to be used are: (i) the ENEIDA Register from Spain (ES), (ii) the ICC Register from the Netherlands (NL), and (iii) SWIBREG from Sweden (SWE). Data from the 3 European IBD registries may be enriched with additional (secondary) data collection information if needed and applicable. The study fulfills the criteria of a non-interventional PASS (category 3) in accordance with the commitment to the EMA and to the MHRA from the United Kingdom.

The study population will include up to 500 consecutive adult patients of any sex with UC and initiating treatment with filgotinib following implementation of the aRMMs after EC's final decision on Article 20 (decision date: 10 March 2023) per registry.

The observational period will be 4 years starting after the EC decision date on Article 20 (i.e. after 10 March 2023). It will include all follow-up time until dropout for the included patients.

Two reports will be generated: an interim report with 2 years of data collection (to be submitted within 9 months after end of interim data collection), and a final study report with 4 years of data collection (to be submitted within 12 months after end of data collection).

*Note*: The end of data collection, i.e. the timepoint by which the analytical dataset to perform the statistical analyses is completely available, is highly correlated with the process of chart abstraction (ENEIDA) or data linkage (SWIBREG). Thus, interim and final study reports will not be available within 9 and 12 months, respectively from the end of the observational periods.

In addition, in the ENEIDA registry, the set-up of ethics approvals, contracts and necessary activities (e.g. trainings) with all individual centers before chart abstraction can begin will likely take up to 2 years, based on prior experience in conducting similar PASS in this registry. It is important to keep this in mind for the scope of the interim report since it will be limited to information readily available in the ENEIDA registry (i.e. without supplementing its information with chart abstraction).

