#### 8.4.2.4.2. Follow-up Visits (Week 12, 24, 52, Year 2, 3, 4, 5, 6, 7, 8, 9, 10)

During follow-up visits, the following information is collected: current clinical disease activity (HBI/SCCAI), biochemical data (Hb, thrombocytes, leucocytes, ALT, alkaline phosphatase, CRP, creatinine, fecal calprotectin), current IBD medication, complications (surgery, hospitalization), AEs (events related to medication and infections), and, if applicable, radiologic and endoscopic information.

Details of variables to be collected in ICC can be found in Annex 3 – Table 5.

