#### Follow-up

Among women starting filgotinib, the number and proportion who become pregnant during follow-up will be reported. Similarly, the number and proportion of patients who have a new

diagnosis of TB during follow-up, a serious acute infection, a diagnosis of viral hepatitis, concomitant treatment with other immunosuppressants, or who are administered a live attenuated vaccine will be reported. In patients with TB, or a serious infection identified during follow-up, it will be assessed whether treatment was stopped or interrupted after the diagnosis. The proportion of patients who have a test for lipids at around 12 weeks since initiation of filgotinib will be reported.

Should a VTE event occur, subsequent changes to filgotinib use will be reported (filgotinib treatment persistence or discontinuation).

Assessment of the filgotinib maintenance dose during follow-up will also be done in the subgroup of patients at high risk of MACE, VTE, or malignancy. In addition, the average daily dose during the maintenance period and the duration of use during the follow-up period will be reported.

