## 8.7.1.2. ICC (NL)

If data are missing, patients are calculated as nonresponders. However, since there is prospective follow-up and centers are alerted if a visit is in the near future, missing data is limited. ICC does not use imputation for missing values.

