Dx date of viral hepatitis	Inconsistently (might be in medical report)	yes	yes (NPR)
Herpes zoster (HZ)	yes (if not available, might be in medical report)	yes	yes (NPR)
Dx date of HZ	Inconsistently (might be in medical report)	yes	yes (NPR)
Screening for TB	yes	no	yes (SmiNet)
Date of screening for TB	yes (possibly in ENEIDA or medical history)	no	yes (SmiNet)
Screening for HZ	yes	no	no
Date of screening for HZ	yes (possibly in ENEIDA or medical history)	no	no
Screening for viral hepatitis	yes	yes	no
Date of screening for viral hepatitis	yes	yes	no
SmPC section 4.4: Special warnings and precautions for use: Haematological abnormalities			
Laboratory measurement of ANC	no (might be in medical report)	no (only total leucocyte count, but it can be added)	yes (currently for <20%)
Date of measurement	no (might be in medical report)	yes (leucocyte count at baseline [week 0])	yes (currently for <20%)
Laboratory measurement of ALC	no (might be in medical report)	no (only total leucocyte count, but it can be added)	yes (currently for <20%)
Date of measurement	no (might be in medical report)		yes (currently for <20%)

Variable	Availability in individual registries yes/no (additional comments)		
	ENEIDA (ES)	ICC (NL)	SWIBREG (SE)
Laboratory measurement of Hb	no (might be in medical report)	yes	yes (currently for <20%)
Date of measurement	no (might be in medical report)	yes	yes (currently for <20%)
SmPC section 4.4: Special warnings and precautions for use: Vaccinations			
Use of live, attenuated vaccines	yes (if not available, might be in medical report)	no (but can be added)	no
Date of vaccine administration	yes		no
HZ vaccination	yes (if not available, might be in medical report)	no (but can be added)	no
Date of vaccine administration	yes		no
SmPC section 4.4: Special warnings and precautions for use: Venous thromboembolism (VTE)			
(Age 65+)	yes	yes	yes
Long-time smoking (current or past) for > 10 years	yes (if not available, might be in medical report)	no (but can be added)	yes (SWIBREG, but suboptimal coverage)
Hx of atherosclerotic CVD	no (might be in medical report)	yes (as part of medical history/comorbidity)	yes (NPR)
Angina	no (might be in medical report)	yes (as part of medical history/comorbidity)	yes (NPR)
Coronary heart disease	no (might be in medical report)	yes (as part of medical history/comorbidity)	yes (NPR)

Variable	Availability in individual registries yes/no (additional comments)		
	ENEIDA (ES)	ICC (NL)	SWIBREG (SE)

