SmPC section 4.4: Special warnings and precautions for use: Infections			

Variable	Availability in individual registries yes/no (additional comments)		
	ENEIDA (ES)	ICC (NL)	SWIBREG (SE)
Acute infection	no (only serious or opportunistic infection can be recorded)	yes	yes (NPR, PDR [prescription of antibiotics])
Dx of acute infection	no	yes	yes (NPR, PDR)
SmPC section 4.4: Special warnings and precautions for use: Viral reactivation	yes (if not available, might be in medical report)		
Viral hepatitis	yes (if not available, might be in medical report)	yes	yes (NPR)
Dx date of viral hepatitis	yes	yes	yes (NPR)
Herpes zoster (HZ)	yes (if not available, might be in medical report)	yes	yes (NPR)
Dx date of HZ	yes	yes	yes (NPR)
SmPC section 4.4: Special warnings and precautions for use: Lipids			
Laboratory measurement of total cholesterol	no (might be in medical report)	no (but will be added)	no
Date of measurement	no (might be in medical report)	(at baseline, week 0), and at follow-up week 12,24, 52 and the year 1, 2, 3)	
Laboratory measurement of HDL	no (might be in medical report)	no (but will be added)	no
Date of measurement	no (might be in medical report)	(at baseline, week 0), and at follow-up week 12,24, 52 and the year 1, 2, 3)	no

Variable	Availability in individual registries yes/no (additional comments)		
	ENEIDA (ES)	ICC (NL)	SWIBREG (SE)
Laboratory measurement of LDL	no (might be in medical report)	no (but will be added)	no
Date of measurement	no (might be in medical report)	(at baseline, week 0), and at follow-up week 12,24, 52 and the year 1, 2, 3)	no
Laboratory measurement of triglycerides	no (might be in medical report)	no (but will be added)	no
Date of measurement	no (might be in medical report)	(at baseline, week 0), and at follow-up week 12,24, 52 and the year 1, 2, 3)	no
Laboratory measurement of HDL:LDL	no (might be in medical report)	no (but will be added)	no
Date of measurement	no (might be in medical report)	(at baseline, week 0), and at follow-up week 12,24, 52 and the year 1, 2, 3)	no
SmPC section 4.4: Special warnings and precautions for use: Haematological abnormalities			
Same as for baseline assessment	no (might be in medical report)	yes	yes (currently for <20%)
SmPC section 4.4: Special warnings and precautions for use: VTE			
VTE event during FU (including PE and deep vein thrombosis)	yes (if not available, might be in medical report)	yes	yes (NPR)
Dx date of VTE	yes	yes	yes (NPR)

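### ICC lipid fields were not yet in the registry 10 months after eligible starts began, and the protocol's two missing-data rules disagree on how early Dutch starters count in the week-12 lipid-test proportion

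*Protocol*

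**What the plan says.** The document is the protocol, "Protocol version: v3.0 Date: 25-January-2024".

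- **Window.** Section 8.1: "The observational period will be 4 years starting after the EC decision date on Article 20 (i.e. after 10 March 2023". Section 8.2.2 admits patients initiated on filgotinib after that date.
- **Outcome.** Section 8.7, Follow-up: "The proportion of patients who have a test for lipids at around 12 weeks since initiation of filgotinib will be reported". Laboratory monitoring during treatment is a named objective (Section 7).
- **ICC lipid fields.** In Annex 3, Table 5, the ICC entries for total cholesterol, HDL, LDL, triglycerides and HDL:LDL all read "no (but will be added". The planned measurement times are "at baseline, week 0), and at follow-up week 12,24, 52 and the year 1, 2, 3". Section 8.4.2.4.2 gives the ICC follow-up panel as "biochemical data (Hb, thrombocytes, leucocytes, ALT, alkaline phosphatase, CRP, creatinine, fecal calprotectin", without lipids.
- **Other ICC fields.** Long-time smoking, live vaccines, hormonal contraceptives and hormone replacement are marked "no (but can be added", which is a possibility and not a commitment.
- **Missing values.** Section 8.7 tabulates missing values but leaves them out of percentages. Section 8.7.1.2, for ICC, says: "If data are missing, patients are calculated as nonresponders".
- **Other registries.** Table 5 shows no lipid data for SWIBREG. For ENEIDA, lipids may be found only in the medical report, and the footnote to the Section 5 milestones says chart abstraction is not done for the interim report.

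**The concern.** A week-12 test can be captured at the scheduled visit only if the form has somewhere to put it. Section 8.7.1.2 expects little missing data because centres are alerted before each visit, but an alert cannot fill a field that does not exist. Whether a patient has a test is naturally scored by whether a record is present, so without a stated rule no record is easily read as no test. The ICC missing-data rule points the same way.

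At stake is the reading of one adherence measure. The ICC figure is the whole of the interim lipid result. If early starters are scored untested, the report would show as prescriber non-compliance something produced by the date the form changed. Section 8.9 does not mention this.

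**Working it through.** The protocol gives no figure for ICC lipid completeness or for ICC accrual, so there is none to reproduce. What follows is calendar arithmetic on stated assumptions.

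**Inputs from the protocol**
- Window opens 10 March 2023 (Section 8.1). Four years = 1461 days; two years, for the interim report, = 731 days.
- Latest date on which the fields are documented as absent: 25 January 2024.
- Test time: 12 weeks = 84 days.
- ICC pre-referral uptake: 54 patients from 12 November 2021 to 10 March 2023 (Section 8.9), which is 483 days. Rate r = 54/483 = 0.1118 per day.
- Target: up to 500 per registry (Section 8.5).

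**Assumptions:** go-live date, accrual shape, true testing rate.

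**Step 1: affected window.** 10 March 2023 to 25 January 2024 = 321 days. Starters in the first 321 − 84 = 237 days (to 2 November 2023) reach week 12 before a go-live on 25 January 2024.

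**Step 2: constant accrual.**
- Final: 237/1461 = 16.2%
- Interim: 237/731 = 32.4%

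**Step 3: linear ramp from r to a four-year total of 500.** Cumulative starters at day t are r·t + b·t²/2, with b = 2(500 − 0.1118 × 1461)/1461² = 0.000315.
- Day 237: 26.5 + 8.9 = 35.4
- Day 731: 81.7 + 84.3 = 166.0
- Final: 35.4/500 = 7.1%
- Interim: 35.4/166.0 = 21.3%

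**Step 4: other scenarios for the final report.**
- Constant accrual with the cap of 500 reached after 3 or 2 years: 21.6% or 32.4%.
- Go-live 25 July 2024, constant accrual over four years: 419/1461 = 28.7%.
- Go-live 25 January 2025, same accrual: 603/1461 = 41.3%. Under the Step 3 ramp: (67.4 + 57.3)/500 = about 25%.

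**Step 5: effect on the reported proportion.** If affected patients are scored untested, reported = true × (1 − share). With an assumed true rate of 60%:

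| Report | Constant accrual | Ramp to 500 |
|---|---|---|
| Final | 0.60 × 0.838 = 50% | 0.60 × 0.929 = 56% |
| Interim | 0.60 × 0.676 = 41% | 0.60 × 0.787 = 47% |

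If the Section 8.7 rule is applied instead, these patients leave the denominator. The estimate is not pulled down, and only the number analysed falls.

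**Step 6: the two rules side by side.** Section 8.7 removes missing values from percentages across the study. Section 8.7.1.2 keeps ICC patients with missing data in, as nonresponders. The study reports no treatment-response outcome to which the second rule could be confined, so the text does not settle which rule governs the lipid proportion.

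**The case against.** The strongest reply is that Section 8.7 already has a rule. Missing values leave the percentage, so early starters shrink the denominator and do not depress the result. Nonresponder is treatment-response language and fits a laboratory test poorly. Section 8.4.2 says ICC biochemical data are extracted from patient files, so an earlier routine test could be entered later. Sections 8.3.1 and 8.3.2 limit variables to what each registry holds, and Section 8.7 sends detailed methods to the statistical analysis plan.

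Much of this stands, and it rules out several stronger readings that a reader might infer:

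- **That early starters cannot be scored.** Back-entry is possible; it is just not promised.
- **That they would necessarily count as untested.** This follows only from applying the ICC rule or from reading no record as no test. The general rule leads elsewhere.
- **That 16% is a minimum.** It needs constant accrual over four years; a ramp from the documented uptake gives about 7%.
- **That the bias is a known number of standard errors.** The protocol gives neither a testing rate nor an ICC sample size for this outcome, and the interim cohort is smaller than the final one.
- **That blank smoking, vaccine or hormone fields would read as absent.** The rule that absence of information means absence of the condition is ENEIDA's (Section 8.7.1.1), not ICC's. ICC already collects smoking status at week 0.

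What the reply does not remove is the conflict between two rules that the protocol itself fixes. Go-live dates and back-entry are also data-collection decisions, best made while records are being filled, and the caveat on availability does not say how a field added midway is to be analysed.

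**Conclusion.** The point holds as a gap combined with a contradiction. On 25 January 2024, 321 days after the window opened, the ICC lipid fields were still to be added, with no date and no plan for earlier starters, and Sections 8.7 and 8.7.1.2 give different answers for them.

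With go-live on the protocol date, the affected share is about 7-16% of the final ICC cohort and 21-32% of the interim cohort across the two accrual patterns. Go-live in January 2025 would take the final share above 40% under constant accrual. None of these is a bound: the true go-live date and the Dutch accrual curve are not in the document. The 60% testing rate is illustrative. The consequence is greatest at interim, where ICC alone supplies lipid data. The matter should be settled before the interim analysis.

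**What to change.** 1. Reconcile Section 8.7 with Section 8.7.1.2: state that the ICC nonresponder rule does not apply to the lipid-test proportion, nor to any field not yet in the form at the visit.
2. In Table 5, give the go-live date of each ICC lipid field.
3. For patients whose week 12 fell before go-live, choose one approach: back-enter the test from the patient file, or restrict the week-12 denominator to patients whose week 12 falls after go-live. Report the number excluded.
4. Apply the same rule to any ICC field marked as possible to add that is in fact added.

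The cost is some wording, one date per field, and either back-entry for early starters or a smaller denominator. As an illustration, at the pre-referral rate the interim ICC cohort would be 0.1118 × 731 = 82, of whom 0.1118 × 237 = 26 are affected, leaving about 55. At an assumed 60%, the standard error would rise from √(0.24/82) = 5.4 points to √(0.24/55) = 6.6 points. Back-entry avoids that loss.
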